### **Detection Limit**

The Detection Limit (DL) for the vaccinia-specific Enzyme-linked Immunosorbent Assay (ELISA) can be found in SOP BN0002809: “Automated ELISA for Detection of Vaccinia Specific Antibodies in Human Sera”, and for the vaccinia-specific Plaque Reduction Neutralization Test (PRNT) can be found in SOP BN0003536: “Human Plaque Reduction Neutralization Test Using Vaccinia Western Reserve”.

### **Geometric Mean Titer**

The Geometric Mean Titer (GMT) is calculated by taking the antilogarithm of the mean of the  $\log_{10}$  transformed titers. Antibody titers below the DL will be given an arbitrary value of “1” (one) for the purpose of this calculation.

### **Seronegative and Seropositive Result**

A seronegative result is a titer below the DL, while a seropositive result is a titer equal to or above the DL.

### **Seroconversion**

Seroconversion is defined as either the appearance of antibody titers  $\geq$  DL for initially seronegative subjects or a doubling or more of the antibody titer compared to baseline titer at Visit 1 for initially seropositive subjects. Seroconversion is not defined for subjects with missing Visit 1 titers.

## **1 Trial Overview**

### **1.1 Trial Description**

This trial is a randomized, open-label Phase II trial to assess the safety and immunogenicity of MVA-BN smallpox vaccine when increasing the number of injections compared to the standard regimen in immunocompromised subjects with HIV infection.

In total, ninety (90) vaccinia-naïve Human Immunodeficiency Virus (HIV) infected subjects will be enrolled in this trial. All subjects will be randomly assigned (1:1:1) to one of three groups (Groups 1-3) to receive:

Group 1:

One injection at Day 0 and Day 28 with 0.5 mL Modified Vaccinia Ankara Strain – Bavarian Nordic (MVA-BN) smallpox vaccine containing at least  $1 \times 10^8$  Tissue Culture Infectious Dose 50% (TCID50) per mL (standard regimen)

Group 2:

Two injections at Day 0 and two injections at Day 28 with 0.5 mL MVA-BN smallpox vaccine each containing at least  $1 \times 10^8$  TCID50 per mL (double dose regimen)

Group 3:

One injection at Day 0 and Day 28 with 0.5 mL MVA-BN smallpox vaccine containing at least  $1 \times 10^8$  TCID50 per mL (standard regimen) and one booster injection at Day 84 (Week 12) with 0.5 mL MVA-BN smallpox vaccine containing at least  $1 \times 10^8$  TCID50 per mL (booster regimen)

### **1.2 Objectives**

#### **1.2.1 Primary Objective**

To assess the safety of MVA-BN smallpox vaccine when increasing the dose or number of injections compared to the standard 2-dose regimen.

#### **1.2.2 Secondary Objectives**

To compare the immunogenicity and safety of three different vaccination strategies of MVA-BN smallpox vaccine.

### **1.3 Trial Population**

Ninety (90) vaccinia-naïve HIV-infected women and men of any ethnicity aged 18 to 45 years who meet all of the inclusion and none of the exclusion criteria are able to enroll into this trial.

## 1.4 Endpoints

### 1.4.1 Primary Endpoint

Occurrence, relationship and intensity of any serious and / or unexpected Adverse Events at any time during the trial.

### 1.4.2 Secondary Endpoints

#### Immunogenicity

- Geometric mean titers (GMTs) after vaccination with MVA-BN smallpox vaccine measured by Enzyme-linked Immunosorbent Assay (ELISA) and Plaque Reduction Neutralization Test (PRNT) at trial Visit 4 for Group 2 compared to Group 1 and Group 3 (combined).
- GMTs after vaccination with MVA-BN smallpox vaccine measured by ELISA and PRNT at trial Visit 7 of Group 3 compared to Visit 4 of Group 1 and Group 2 (separately).
- GMTs after vaccination with MVA-BN smallpox vaccine measured by ELISA and PRNT at six months Follow-up 1 (FU 1) and one year FU 2 Visit of Group 3 compared to respective FU Visits of Group 1 and Group 2 (separately).
- Seroconversion after vaccination with MVA-BN smallpox vaccine measured by ELISA and PRNT at trial Visit 4 of Group 2 compared to Group 1 and 3 (combined).
- Seroconversion after vaccination with MVA-BN smallpox vaccine measured by ELISA and PRNT at trial Visit 7 of Group 3 compared to Visit 4 of Group 1 and Group 2 (separately).
- Seroconversion after vaccination with MVA-BN smallpox vaccine measured by ELISA and PRNT at six months FU 1 and one year FU 2 Visit of Group 3 compared to respective FU Visits of Group 1 and Group 2 (separately).
- GMTs and seroconversion after vaccination with MVA-BN smallpox vaccine measured by ELISA and PRNT at all other immunogenicity sampling points (Visit 1, 3, 4, six months FU 1, one year FU 2) of Group 2 and 3 (separately) compared to Group 1.
- GMTs and seroconversion after vaccination with MVA-BN smallpox vaccine measured by ELISA and PRNT at trial Visit 6 and 7 of Group 3.

#### Safety and Reactogenicity

- Occurrence, relationship to the trial vaccine and intensity of any Adverse Event of Special Interest (AESI).
- Occurrence of any Grade 3 or 4 Adverse Events (AEs) probably, possibly or definitely related to the trial vaccine within 28 days after each vaccination.
- Occurrence, relationship to the trial vaccine and intensity of unsolicited non-serious AEs within 28 days after each vaccination.

- Occurrence, intensity and duration of solicited local AEs (redness, swelling, induration, pruritus and pain) during the 8-day period (day of vaccination and the following seven days) after each vaccination.
- Occurrence, relationship to the trial vaccine, intensity and duration of solicited general AEs (pyrexia, headache, myalgia, nausea, fatigue and chills) during the 8-day period (day of vaccination and the following seven days) after each vaccination.
- Change in CD4 T cell counts in Human Immunodeficiency Virus (HIV)-infected subjects two weeks after each vaccination.

### **1.5 Interim Analysis**

No interim analysis is planned for this trial.

### **1.6 Data Safety Monitoring Board**

The Data Safety Monitoring Board (DSMB) is an independent expert panel appointed by the sponsor. This board is in charge of surveying the subjects' safety throughout the course of the trial. All relevant roles, responsibilities and procedures for the DSMB are described in the DSMB charter. Initial review will be done on summaries of the safety, disposition and demographic data prepared by the [REDACTED] biostatistician and will be provided directly and securely to the DSMB members.

A summary of the activities and recommendations of the DSMB will be provided in the CSR.

## 2 Trial Design

Visit (V)	SCR	V1	V2	V3	V4	V5	V6*	V7*	V8*	FU 1	FU 2
Day / Visit +... Day	-28--1	0	V1+ 12-16	V1+ 28-35	V3+ 12-16	V3+ 28-35	V1+ 84-96	V6+ 12-16	V6+ 28-35	V3 (V6*)+ 182-210	V3 (V6*)+ 364-392
Target week	- 4	0	2	4	6	8	12	14	16	30 (38*)	56 (64*)
Procedures											
Informed consent & HIPAA	X										X 
Check incl. / excl. criteria	X	X									
Medical History/HIV specific medical history	X										
Check criteria for withdrawal of next vaccination				X			X				
Assessment for previous smallpox vaccination including check for a scar	X										
Complete physical exam	X										
Evaluation of vital signs	X	X	X	X	X	X	X	X	X	X	X
Calculate individual cardiac risk factor	X										
Evaluation of family cardiac risk factors	X										
Targeted physical exam incl. auscultation of the heart and lung		X	X	X	X	X	X	X	X	X	X
ECG 	X		X		(X) 			(X) 			
Recording of prior and concomitant medication	X	X	X	X	X	X	X	X	X		
Counseling on avoidance of pregnancy for WOCBP 	X	X		X			X				
AE/SAE/AESI recording	X	X	X	X	X	X	X	X	X	X 	X 
Lab											
Pregnancy test for WOCBP 	X	X		X		X	X		X		

Visit (V)	SCR	V1	V2	V3	V4	V5	V6*	V7*	V8*	FU 1	FU 2
Day / Visit +... Day	-28--1	0	V1+ 12-16	V1+ 28-35	V3+ 12-16	V3+ 28-35	V1+ 84-96	V6+ 12-16	V6+ 28-35	V3 (V6*)+ 182-210	V3 (V6*)+ 364-392
Target week	- 4	0	2	4	6	8	12	14	16	30 (38*)	56 (64*)
Obtaining blood for safety lab 	X		X		X			X		(X) 	(X) 
Total, HDL and LDL cholesterol	X										
Troponin I testing 	X		X		X			X			
Serum collection for immunogenicity testing		X		X	X		X	X		X	X
CD4 count	X		X		X			X	X	X	X
Viral Load 	X		X								
Vaccination											
Vaccine administration & Subject observation		X		X			X				
Recording of immediate AEs		X		X			X				
Handout of memory aid		X		X			X				
Collection of memory aid			X		X			X			
Examination of injection site			X		X			X			

\*Visits performed for subjects in Group 3 only

(x),  Only to be performed if clinically indicated, i.e. in the presence of cardiac signs or symptoms.

 New Serious Adverse Events (SAEs)/ AESIs and changes to SAEs/AESIs/AEs ongoing at V5 (Group 1/2) or V8 (Group 3) only.

 At SCR, a serum test must be performed. At other visits, a urine pregnancy test will be performed.

 If clinically indicated, additional safety measures can be taken at any other trial visits or at unscheduled visits.

 N.A.

 Review of acceptable contraceptive methods and recent menstrual history with Women of Child Bearing Potential (WOCBP).

 Viral load will be determined during treatment period if clinically indicated.

 FU 2 procedures added after initial trial entry informed consent; i.e. subjects need to sign updated informed consent form at or before FU 2.

## 3 Statistical Methods

### 3.1 Planned Sample Size

In addition to the below sample size calculations for the immunogenicity endpoints, a sample size of 30 per treatment group also allows for the detection of AEs with an incidence of at least 1 in 10 with a probability of detection of at least 95%.

A sample size of 30 in each group will have 80% power to detect a difference in means of 0.74 x standard deviation (SD) using a two-group t-test with a 5% two-sided significance level. This means that a difference  $\Delta$  can be detected with  $\Delta / SD > 0.74$ . Taking into account the SD of 0.85 for the  $\log_{10}$  PRNT titers the detection of a  $\log_{10}$  PRNT difference of 0.629 can be detected (or a difference in titers on the original titer scale by a factor of 4). For the ELISA where the  $\log_{10}$  SD is at most 0.42 a difference of 0.311 can be detected, i.e. a difference in titers by a factor of 2 on the original scale can be detected.

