### 9.2 Sample Size Calculation

In addition to the below sample size calculations for the immunogenicity endpoints, a sample size of 30 per group also allows for the detection of AEs with an incidence of at least 1 in 10 with a probability of detection of 95% or more.

A sample size of 30 in each group will have 80% power to detect a difference in means of  $0.74 \times$  standard deviation (SD) using a two-group t-test with a 5% two-sided significance level. This means that a difference  $\Delta$  can be detected with  $\Delta / SD > 0.74$ . Taking into account the relative SD of 0.85 for the log10 PRNT titers the detection of a log10 PRNT difference of 0.629 can be detected (or a four-fold increase in titers on the original titer scale). For the ELISA where the log10 SD is at most 0.42 a difference of 0.31 can be detected, i.e. a two-fold increase in titers can be detected.

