#### 3.2.2 Per Protocol Set (PPS)

This is the subset of subjects in the FAS who have received all vaccinations, completed all visits of the active trial phase (Visit 1 to Visit 5 and additionally Visit 6 to Visit 8 for Group 3; see [Table 1](#)) and adhered to all protocol conditions. Subjects with only minor (not relevant) protocol deviations are included into this dataset.

The decision whether a protocol deviation is major or not will be made on a case-by-case basis in a data review meeting (DRM) prior to database lock.

Examples of major protocol violations are:

1. Premature discontinuation of the trial before Visit 5 for Groups 1 and 2 or Visit 8 for Group 3 (the question “prematurely terminated the trial?” is answered with “yes” even where no other reason exists to exclude the subject from further participation in accordance with the protocol)
2. Subject did not meet all of the inclusion criteria
3. Subject met one or more of the exclusion criteria
4. Withdrawal from the second and/or third vaccination

- 
5. Major vaccine preparation and administration deviation from specification as given in the protocol including cases where the subject fulfils at least one of the criteria specified in the protocol for withdrawal from vaccination
  6. Major deviations of the visit window as determined during the DRM(s)
  7. Unallowed prior or concomitant medication
  8. Missing humoral immune response data (ELISA and PRNT) at Visit 1 or 4 (or Visit 7 for Group 3)

A classification of all subjects in the FAS for major protocol deviations will be performed at the time of the DRM.

The main analysis of the immunogenicity endpoints will be performed on the PPS. The same statistical procedures will also be applied to the FAS.

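### The 80% power for immunogenicity is computed correctly but holds only if all 30 subjects per group are evaluable; the four-fold and two-fold wording rounds it favourably

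*SAP*

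**What the plan says.** SAP 3.1 says that 30 subjects in each group "will have 80% power to detect a difference in means" of 0.74 SD, "using a two-group t-test with a 5% two-sided significance level". With a log10 SD of 0.85 for PRNT this becomes a log10 difference of 0.629, described as "a difference in titers on the original titer scale by a factor of 4". For ELISA, where the log10 SD is given as at most 0.42, it becomes 0.311, described as a factor of 2. Protocol 9.2 has the same calculation (0.31 for ELISA) and words the PRNT result as "or a four-fold increase in titers on the original titer scale".

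Protocol 5.1 plans 30 enrolled per group, 90 in total. Neither document adds subjects for loss or gives an expected rate of dropout or exclusion.

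SAP 3.2.2 states: "The main analysis of the immunogenicity endpoints will be performed on the PPS". The PPS requires all vaccinations, all active-phase visits (through Visit 5, or Visit 8 in Group 3) and no major deviation. A missing titer at Visit 1 or 4, or at Visit 7 in Group 3, is listed as an example of a major violation. Protocol 9.3 and SAP 3.3.1 rule out imputing titers. The same analyses are repeated on the FAS.

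SAP 1.4.2 lists first the Visit 4 comparison of Group 2 with Groups 1 and 3 combined. The other between-group comparisons set single groups against each other.

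**The concern.** The power statement describes 30 analysed subjects per group. The plan enrols 30 and then makes a smaller set the main one. If the calculation has no margin, its 80% does not apply to the analysis it is meant to justify.

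The fold figures raise a second, smaller question. A clinical reader will remember four-fold and two-fold rather than 0.629 and 0.311. If 80% power belongs to somewhat larger folds, an inconclusive GMT ratio may be read as stronger evidence against a four-fold difference than it is.

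Third, one stated figure stands for two designs: 30 vs 30 for most contrasts, and 30 vs 60 for the first-listed one.

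**Working it through.** **Inputs.** From SAP 3.1: two-sided 5% two-group t-test, d = 0.74, log10 SD 0.85 (PRNT) and at most 0.42 (ELISA). From Protocol 5.1: 30 enrolled per group. The sizes 27 and 24 are my assumptions (10% and 20% loss), because the documents give no rate.

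**Formula.** For groups of n1 and n2 and standardised difference d, the test statistic is noncentral t with df = n1 + n2 − 2 and noncentrality λ = d / √(1/n1 + 1/n2). Power is the probability that |t| exceeds the 97.5% point of central t.

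**Step 1: the plan's own figure.** For 30 vs 30 and d = 0.74, λ = 0.74 × √15 = 2.866 with df 58, and power is 80.5%. The smallest n per group reaching 80% at d = 0.74 is 30. The conversions are also right: 0.74 × 0.85 = 0.629 and 0.74 × 0.42 = 0.311.

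**Step 2: the fold wording.** 10^0.629 = 4.26 and 10^0.311 = 2.05. At exactly the stated factors with 30 vs 30:
- PRNT: d = log10(4)/0.85 = 0.602/0.85 = 0.708; power 77.0% (78.3% by normal approximation). Reaching 80% by the t-test needs 33 per group.
- ELISA: d = log10(2)/0.42 = 0.301/0.42 = 0.717; power 77.9% (79.3% by normal approximation). Reaching 80% needs 32 per group. This power is a floor, since 0.42 is an upper bound on the SD. The detectable d at 80% power with 30 per group is 0.736, so two-fold already has 80% power if the SD is 0.301/0.736 = 0.409 or less.

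**Step 3: fewer evaluable subjects, equal groups.**

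| Evaluable per group | Power at 0.74 SD | Power at 4-fold PRNT | Power at 2-fold ELISA (SD 0.42) | Detectable d at 80% | PRNT fold at 80% | ELISA fold at 80% |
|---|---|---|---|---|---|---|
| 30 | 80.5% | 77.0% | 77.9% | 0.736 | 4.22 | 2.04 |
| 29 | 79.1% | 75.5% | 76.5% | 0.749 | 4.33 | 2.06 |
| 27 (assumed 10% loss) | 76.1% | 72.4% | 73.4% | 0.777 | 4.58 | 2.12 |
| 24 (assumed 20% loss) | 70.9% | 67.1% | 68.1% | 0.826 | 5.04 | 2.22 |

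The folds in the last two columns are 10^(d × SD). The first row is slightly below 4.26 and 2.05 because the exact detectable d, 0.736, is a little under the plan's rounded 0.74. A single exclusion in only one group (30 vs 29) gives λ = 0.74 / √(1/30 + 1/29) = 2.842 with df 57, and power 79.8%.

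**Step 4: the pooled Visit 4 contrast.**

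| Group 2 vs Groups 1+3 | Power at 4-fold PRNT | Power at 2-fold ELISA (SD 0.42) |
|---|---|---|
| 30 vs 60 | 88.0% | 88.7% |
| 27 vs 54 (assumed 10% loss) | 84.3% | 85.2% |
| 24 vs 48 (assumed 20% loss) | 79.8% | 80.7% |

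At 30 vs 60 the detectable d at 80% power is 0.633, that is, 3.45-fold for PRNT and 1.85-fold for ELISA.

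**The case against.** The strongest reply is that the sponsor's claim is attached to 0.74 SD, and for 0.74 SD it is right. Four and two are nearest-integer roundings of 4.26 and 2.05, and the unrounded log10 values stand in the same sentences. The literal shortfall is 3 points for PRNT and 2 for ELISA, less by the normal approximation, and the ELISA figure is a worst case. This stands, and the rounding alone would be a minor matter.

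It can also be said that attrition may be slight. Subjects count as enrolled only once injected (SAP, General Definitions), so losses before the first vaccination do not erode the 30. Minor deviations stay in the PPS, major ones are judged case by case, and missing follow-up visits are minor. All of that is correct, and it means the loss rate cannot be derived from the documents. It does not create a margin. Keeping a subject who missed FU 1 or FU 2 in the PPS also supplies no titer there, so with no imputation the follow-up contrasts can have fewer evaluable subjects than the PPS. Group 3, which appears in most of the single-group contrasts, has three further visits and a third vaccination to complete before it qualifies.

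Finally, the primary endpoint is safety and its analysis descriptive. Immunogenicity is secondary, and SAP 3.5.8 reports GMT ratios and seroconversion differences, mainly with 95% confidence intervals; it names no hypothesis test or success criterion. The intervals will show the precision actually reached. This limits the consequence. It does not make the power statement accurate for the main analysis set.

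A reader might infer that 30 per group was miscalculated, or that the trial is underpowered throughout. The documents support neither. The base calculation reproduces, the first-listed contrast has more power than stated, and the size has a separate safety basis that also reproduces: 1 − 0.9^30 = 95.8% for seeing an event of 1 in 10 incidence.

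**Conclusion.** The concern holds in a limited form. The 80% is correct for 30 evaluable subjects per group and 0.74 SD, but the plan enrols exactly the minimum and analyses a subset. Any exclusion takes the 30-vs-30 contrasts below 80%: by under 2 points at 29 per group, about 4 at 27 and about 9 at 24. The last two rest on assumed loss rates, and all figures take the plan's SDs as given and equal between groups.

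The four-fold and two-fold labels overstate slightly: power there is 77% and at least 78%, even with all 30. The pooled Visit 4 contrast is understated. It has 88% and 89% power at those factors and keeps about 80% under an assumed 20% loss.

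The stated sensitivity should be corrected because it is the plan's only justification of size for immunogenicity. No planned analysis, analysis set or conclusion is invalidated, and there is no case here for more subjects.

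**What to change.** Restate Protocol 9.2 and SAP 3.1 in three parts:

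1. With 30 evaluable subjects per group, 80% power for a difference of about 4.3-fold in PRNT (log10 SD 0.85) and about 2.05-fold in ELISA (log10 SD 0.42, an upper bound).
2. The detectable folds at 80% power for a range of PPS sizes labelled as assumptions, for example 4.6-fold and 2.1-fold at 27 per group, and 5.0-fold and 2.2-fold at 24 per group.
3. A separate figure for Group 2 vs Groups 1 and 3 combined at Visit 4: with 30 vs 60 evaluable, 80% power at about 3.5-fold (PRNT) and 1.85-fold (ELISA).

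The cost is a few sentences. Enrolment, analysis sets and methods stay as they are. The only downside is that the stated figure for the separate-group contrasts becomes slightly less favourable.

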### 3.2 Analysis Populations

#### 3.2.1 Full Analysis Set (FAS)

This is the subset of subjects who received at least one injection and for whom any data are available.

The main analysis of safety will be performed on this analysis set.

#### 3.2.2 Per Protocol Set (PPS)

This is the subset of subjects in the FAS who have received all vaccinations, completed all visits of the active trial phase (Visit 1 to Visit 5 and additionally Visit 6 to Visit 8 for Group 3; see [Table 1](#)) and adhered to all protocol conditions. Subjects with only minor (not relevant) protocol deviations are included into this dataset.

The decision whether a protocol deviation is major or not will be made on a case-by-case basis in a data review meeting (DRM) prior to database lock.

Examples of major protocol violations are:

1. Premature discontinuation of the trial before Visit 5 for Groups 1 and 2 or Visit 8 for Group 3 (the question “prematurely terminated the trial?” is answered with “yes” even where no other reason exists to exclude the subject from further participation in accordance with the protocol)
2. Subject did not meet all of the inclusion criteria
3. Subject met one or more of the exclusion criteria
4. Withdrawal from the second and/or third vaccination

- 
5. Major vaccine preparation and administration deviation from specification as given in the protocol including cases where the subject fulfils at least one of the criteria specified in the protocol for withdrawal from vaccination
  6. Major deviations of the visit window as determined during the DRM(s)
  7. Unallowed prior or concomitant medication
  8. Missing humoral immune response data (ELISA and PRNT) at Visit 1 or 4 (or Visit 7 for Group 3)

A classification of all subjects in the FAS for major protocol deviations will be performed at the time of the DRM.

The main analysis of the immunogenicity endpoints will be performed on the PPS. The same statistical procedures will also be applied to the FAS.

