## 4 Trial Design

### 4.1 Experimental Design

Randomized, open-label Phase II trial to assess the safety and immunogenicity of MVA-BN® smallpox vaccine when increasing the number of injections compared to the standard regimen in immunocompromised subjects with HIV infection

In total, 90 vaccinia-naïve subjects will be enrolled in this trial (see [Table 4](#)). All subjects will be randomly assigned (1:1:1) to Group 1, Group 2 or Group 3. Group 1 will receive the standard regime – two vaccinations at Day 0 and Day 28. Group 2 will receive two injections at each vaccination day in the standard schedule and Group 3 will receive the standard regime and an additional early boost 12 weeks after the first dose of the standard vaccination schedule with MVA-BN® smallpox vaccine.

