##### Procedure:

If a subject did not receive the second trial vaccination the reason for this decision must be recorded in the eCRF. Visit 3 and Visit 4 are not required and the procedures below should be followed:

- Visit 5 procedures have to be performed 28 to 35 days after last vaccination

- FU 1 procedures have to be performed 182 to 210 days after last vaccination
- FU 2 procedures have to be performed 364 to 392 days after last vaccination.

If a subject from treatment Group 3 did not receive the second or booster vaccination the reason for this decision must be recorded in the eCRF. Visits 6, 7 and 8 are not required and the procedures below should be followed:

- FU 1 procedures have to be performed 182 to 210 days after last vaccination.
- FU 2 procedures have to be performed 364 to 392 days after last vaccination.

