#### Per Protocol Set (PPS):

This is the subset of subjects in the FAS who have received all vaccinations, completed all visits of the active trial phase (Visit 1 to Visit 5 and additionally Visit 6 to Visit 8 for Group 3) and

adhered to all protocol conditions. Subjects with only minor (not relevant) protocol deviations are included into this dataset.

The decision whether a protocol deviation is major or not for the classification of subjects into the various subsets will be made on a case-by-case basis in a data review meeting prior to database lock.

The main analysis of the immunogenicity endpoints will be performed on the PPS. The same statistical procedures will also be applied to the FAS.

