### Subjects Receiving All Vaccinations

A subject received all doses of trial vaccination according to the randomized group assignment if a date of drug administration is given for the vaccination at Visit 1, Visit 3, and in addition in Group 3 for the vaccination at Visit 6, and no major deviation is recorded on the electronic Case Report Form (eCRF).

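### The single per-protocol set removes Group 3 subjects from the main Visit 3 and Visit 4 comparisons for booster-period events that Groups 1 and 2 cannot have

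*SAP*

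**What the plan says.** SAP 3.2.2 defines one PPS: FAS subjects who "received all vaccinations, completed all visits of the active trial phase (Visit 1 to Visit 5 and additionally Visit 6 to Visit 8" (the latter Group 3 only), without major deviations. The PPS paragraph of Protocol 9.3 has the same rule ("completed all visits of the active trial phase (Visit 1 to Visit 5 and additionally Visit 6 to Visit 8 for Group 3"). Among the SAP's examples of major violations are discontinuing before Visit 5 (Groups 1 and 2) or Visit 8 (Group 3), "Withdrawal from the second and/or third vaccination", and "Missing humoral immune response data (ELISA and PRNT) at Visit 1 or 4 (or Visit 7 for Group 3". The SAP definition of a subject who received all vaccinations requires Visits 1 and 3, and "in addition in Group 3 for the vaccination at Visit 6".

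The role of the set is explicit: "The main analysis of the immunogenicity endpoints will be performed on the PPS". The same procedures are then repeated on the FAS. SAP 3.5.8 compares:

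- Group 2 with Groups 1 and 3 combined at Visit 4 (GMT and seroconversion);
- Group 1 with Groups 2 and 3 separately at Visit 3, Visit 4 and the follow-up visits, and at Visit 1 for GMT only;
- Group 3 at Visit 7 with Groups 1 and 2 separately at Visit 4.

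Neither the text nor the table index has a visit-specific PPS.

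On design, Protocol 4.1 says that "Group 3 will receive the standard regime and an additional early boost 12 weeks after the first dose", so Groups 1 and 3 are treated alike until the booster. If the booster is withheld, Protocol 4.2.5 says "Visits 6, 7 and 8 are not required and the procedures below should be followed".

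**The concern.** Groups 1 and 3 can be pooled at Visit 4 because they have had the same vaccinations by then. The PPS filters one half of that pool on events that come weeks after the sample.

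The plainest case is a Group 3 subject who received both standard vaccinations, has complete Visit 1 to 5 data, and has the booster withheld and Visits 6 to 8 omitted as Protocol 4.2.5 provides. That subject's valid Visit 3 and Visit 4 titres leave the main analysis. A Group 1 subject with the same record to Visit 5 stays in.

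If the reasons for losing the booster or the later visits are related to antibody response, three main estimates are affected: the Visit 4 comparison of double dose with standard regimen, and the Group 1 versus Group 3 comparisons at Visits 3 and 4. The Visit 1 GMT comparison is formally affected too. It matters little, because it uses pre-vaccination samples from vaccinia-naïve subjects.

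**Working it through.** **1. How long each group must stay compliant after its sample.** Visit windows from Protocol 1.6 and 4.2.2, with Visit 1 as Day 0:

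- Visit 3 = Day 28 to 35; Visit 4 = Visit 3 + 12 to 16 = Day 40 to 51; Visit 5 = Visit 3 + 28 to 35.
- Visit 6 = Day 84 to 96; Visit 7 = Visit 6 + 12 to 16; Visit 8 = Visit 6 + 28 to 35 = Day 112 to 131.

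| Sample | Groups 1 and 2, to Visit 5 | Group 3, to Visit 8 |
|---|---|---|
| Visit 3 | 28 to 35 days | 112 − 35 = 77 to 131 − 28 = 103 days |
| Visit 4 | 28 − 16 = 12 to 35 − 12 = 23 days | 112 − 51 = 61 to 131 − 40 = 91 days |
| Visit 7 | not applicable | 28 − 16 = 12 to 35 − 12 = 23 days |

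Same-visit comparisons at Visits 3 and 4 are asymmetric. The Visit 7 (Group 3) versus Visit 4 (Groups 1 and 2) comparison is not: both sides are held to a visit 12 to 23 days after the compared sample.

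**2. The plan's own figure.** SAP 3.1 gives 80% power at 0.74 SD with 30 per group (two-sided 5% t-test). The noncentral t gives 80.5%. With the SAP's log10 SDs, 0.74 × 0.85 = 0.629 (PRNT, 4.26-fold) and 0.74 × 0.42 = 0.311 (ELISA, 2.05-fold). The figure reproduces, and these SDs are used below.

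**3. Precision.** The documents give no exclusion rate. Suppose 3 or 6 of 30 Group 3 subjects are lost to booster-period events alone. Power for Group 3 versus Group 1 at 0.74 SD falls from 80.5% to 78.3% or 75.6%. The difference detectable with 80% power for Group 2 versus Groups 1 and 3 moves from 0.633 SD to 0.639 or 0.646 SD. These losses are small.

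**4. Selection.** Assume a standardised log titre z ~ N(0,1) and P(excluded) = 1/(1 + exp(−(a − bz))), with a set to give exclusion rate p. Two scenarios span the assumed range: p = 10%, b = 0.5 (odds ratio 1.65 per SD lower titre) and p = 20%, b = 1.0 (odds ratio 2.72). Numerical integration gives a mean m for retained Group 3 subjects of 0.049 SD and 0.173 SD. With n3 = 27 or 24 retained and no true difference:

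- Visit 4 ratio, Group 2 to Groups 1 and 3 = 10^(−SD × n3 × m / (30 + n3)).
- PRNT: 10^(−0.0197) = 0.956 and 10^(−0.0654) = 0.860. ELISA: 0.978 and 0.928.
- PRNT 95% CI half-width on log10, t × 0.85 × √(1/30 + 1/(30 + n3)): 0.381 and 0.385 (factors 2.41 and 2.43). Shift as a share: 0.0197/0.381 = 5.2% and 0.0654/0.385 = 17.0%.
- Group 3 to Group 1, PRNT = 10^(0.85 × m): 1.10 and 1.40, against CI factors of 2.83 and 2.93 (9% and 32% of the half-width).
- Per subject: excluding one Group 3 subject 1 SD below the mean multiplies the pooled PRNT ratio by 10^(−0.85/59) = 0.967.

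If b = 0, every ratio is 1. If higher responders are the ones lost, the pooled PRNT ratios become the reciprocals, 1.05 and 1.16.

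**The case against.** **The rule can be called even-handed.** Each group is followed to the visit 28 to 35 days after its own last scheduled vaccination. This is a fair description and it is decisive for Visit 7 versus Visit 4, where step 1 shows matched conditions. It does not help at Visits 3 and 4, where samples from the same visit are compared and only Group 3 carries the later conditions.

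**The FAS repeat keeps every disputed titre.** It needs one injection only, and each PPS comparison table has an FAS counterpart. This stands and limits the damage. But the FAS is the repeat and not the main set, and it readmits subjects with early deviations, so it is not a per-protocol estimate at Visit 4.

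**The data review meeting decides case by case.** That could rescue a subject with a missed Visit 8 or missing Visit 7 titres. It cannot rescue a subject without the booster, who fails the definition itself.

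**A fixed cohort has value.** The Group 3 rise from Visit 4 to Visit 7 is best read in the same people. This also stands, and the fix has to respect it.

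**A wider reading is tempting:** that every group is wrongly selected on events after the sample, so membership should be judged only up to the visit analysed. The documents do not support this. The Visit 5 condition falls on all three groups alike. Dropping it for Groups 1 and 2 while holding Group 3 to Visit 8 would create a one-sided selection in the Visit 7 versus Visit 4 comparison that does not exist now.

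**Conclusion.** The asymmetry is real and follows directly from the definitions. In the main Visit 3 and Visit 4 comparisons, Group 3 alone is filtered on the booster, Visits 6 to 8 and Visit 7 titres.

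Its effect is unknown. Under the assumed range (3 to 6 of 30 excluded, odds ratio 1.65 to 2.7 per SD lower titre) the null pooled PRNT ratio moves to 0.96 to 0.86, at most 17% of the log CI half-width. Neither the exclusion rate nor the link with titre comes from the documents.

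A reader might infer that the plan inflates the pooled comparator and so understates the double-dose effect. The documents do not fix that direction. An adverse event can lead to the booster being withheld (Protocol 4.2.5), and Protocol 2.6.3 expects lower reactogenicity with impaired immunity, so better responders could be the ones lost. Nor does the point touch the primary endpoint, which is safety, descriptive and analysed on the FAS.

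The weight is minor: the endpoints are secondary, they are reported as estimates with intervals and no pass/fail test, and a full FAS repeat is planned. The change is still worth making because it is cheap and keeps valid data in the main analysis.

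**What to change.** Add to SAP 3.2.2:

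> *For comparisons at Visits 1, 3 and 4 among samples from the same visit, the third-vaccination, Visit 6-8 and Visit 7 titre requirements, and deviations arising after Visit 5, do not apply to Group 3; Group 3 is judged on the same Visit 1-5 conditions as Groups 1 and 2. The PPS as defined above is unchanged for Groups 1 and 2 at all visits, and for Group 3 at Visits 6, 7, FU 1 and FU 2, including the Visit 7 (Group 3) versus Visit 4 (Groups 1 and 2) comparison.*

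Record the change in SAP 3.6, which now lists no alterations from the protocol, or amend Protocol 9.3. An amendment needs the written approvals set out in Protocol 14. Keep the FAS repeat as planned.

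The cost is one extra Group 3 flag at the data review meeting already planned, with no new subjects or samples. Group 3 PPS membership will differ between Visits 1 to 4 and Visits 6 onward. The booster rise in the PPS charts should therefore be read in the unchanged full PPS, with a footnote saying so; the GMT tables already plan to show n by visit.
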